7.5. Adjustments for Multiple Comparisons

The study has one primary objective that will be evaluated with statistical testing. The primary objective will be evaluated with statistical testing at the $\alpha=0.05$ level after all subjects in the Treated Analysis Set have completed the 3-Month Visit. The secondary objectives are not alpha-controlled; they will be characterized but not evaluated with statistical testing.

7.6. Demographic and Other Baseline Characteristics

Demographic and other baseline characteristics will be summarized for the Enrolled, Trialed, and/or Treated Analysis Sets (section 7.1.3) as appropriate. Subjects with missing or unknown demographic data will be excluded from the relevant analysis, with a count of subjects with missing data provided. Listings of all demographic and baseline characteristics will be included.

7.6.1. Demographics

Age at consent, in years, will be calculated as the difference between the first consent date and the subject's date of birth, using the following formula: $(\text{CONSENTDATE} - \text{BIRTHDATE})/365.25$.

Age will be summarized using descriptive statistics such as mean, standard deviation, minimum, and maximum.

Categorical demographics (sex, ethnicity, and race) will be summarized as counts and percentages. If more than one race is selected for a subject, this be counted as "Multiple" in the race summary, and additional details will be provided separately for these subjects.

7.6.2. Baseline Characteristics

Years from onset of chronic intractable pain to enrollment will be calculated as:

Year of first consent date – Year of onset for chronic intractable pain of the low back and leg

Years from pain onset will be summarized using descriptive statistics such as mean, standard deviation, minimum, and maximum.

Primary diagnosis will be summarized as a count and percentage.

The number of prior surgical procedures will be counted per subject, with each row in Surgical History being counted as one procedure. For subjects where it is indicated there is no history of surgical procedures, the number of procedures will be 0. Number of prior procedures will be summarized using descriptive statistics such as mean, standard deviation, minimum, and maximum. Additionally, a frequency distribution will be provided summarizing the number of subjects with 0, 1, 2, etc. prior surgical procedures.

The number of pain medications with a start date on or before the date of the subject's baseline pain assessment, where the medication is ongoing or has an end date after the date of baseline pain assessment will be counted per subject. For subjects where it is indicated there are no medications with a start date on or before the date of baseline pain assessment, the number of medications will be 0. Number of pain medications will be summarized using descriptive statistics such as mean, standard

deviation, minimum, and maximum. Additionally, a frequency distribution will be provided summarizing the number of subjects with 0, 1, 2, etc. medications at enrollment.

7.6.3. Baseline Assessments

Assessments collected at baseline will be summarized as follows.

The visual analog scale (VAS) for overall pain (low back and leg), low back pain, and leg pain, will be summarized using descriptive statistics such as mean, standard deviation, minimum, and maximum. The distribution in 10-point increments from 50 to 100 will also be shown for each VAS measurement.

7.7. Treatment Characteristics

Device exposure will be quantified and summarized separately for the Trialed, Implanted, and Treated Analysis Sets. Amount of exposure will be summarized using descriptive statistics such as mean, standard deviation, sum, minimum, and maximum.

For all subjects in the Trialed Analysis Set, the number of days of device exposure will be calculated as:

$$\text{Date of trialing leads explant} - \text{Date of Trialing Day 0}$$

If the date of trialing leads explant is unavailable, and the subject discontinues from the study during the trial, study exit date will be used in place of the trialing leads explant date.

For all subjects in the Implanted Analysis Set, the number of days of device exposure between implant and device activation will be calculated as:

$$\text{Date of Device Activation Visit} - \text{Date of Implant Visit}$$

If a subject discontinues from the study after implant prior to the Device Activation Visit, the study exit date will be used in place of the Device Activation Visit date.

Months of device exposure for subjects in the Treated Analysis Set will be calculated as:

$$[(\text{Cut-Off Date} - \text{Date of Device Activation Visit})/365.25]*12$$

Where Cut-off Date for each subject is, in order of priority:

- (1) the date of permanent system explant, if applicable, or
- (2) the date of study exit, or
- (3) the most recent follow-up visit (scheduled or unscheduled).

Programming data from the Neuro Programmer Upload (NPU) database will be evaluated for subjects in the Treated Analysis Set to determine whether subjects ever received physician preference stimulation settings (ie, non-HD settings) during the study. For subjects who received physician preference stimulation settings, the months from Device Activation to first use of physician preference stimulation settings will be quantified.

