## 4.2. Purpose

The purpose of this study is to evaluate the efficacy of spinal cord stimulation (SCS) therapy using HD stimulation parameters while targeting a specific anatomical location.

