### 9.8. Unscheduled Visits:

Unscheduled visits may occur if programming changes are required to correct programming errors, to reprogram to optimize pain control (see Reprogramming Instructions in section 9.6), or for an AE. Whenever feasible, subjects should have their devices interrogated. If a subject was experiencing  $\geq 50\%$  reduction in pain at a previous visit and no longer is, a fluoroscopy/x-ray annotated with vertebral marker(s) may be taken to assess for possible lead migration.

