## 10.4. Risk-Benefit Rationale

Neurostimulation therapies, such as SCS, are used as an aid in the management of chronic, intractable pain that cannot be effectively managed with medications and/or other conservative treatments alone. Patients considered for neurostimulation therapy have typically had pain of long duration and have failed multiple therapeutic paths. Findings from clinical studies documented in published literature suggest that T9/T10 has been a common location to target stimulation for chronic back and leg pain.

Medtronic has carefully designed and tested the RestoreSensor SureScan MRI and Intellis AdaptiveStim Neurostimulation Systems to ensure the safety and performance for the treatment of chronic, intractable pain. Medtronic has completed an extensive risk analysis to ensure the identification of potential hazards and subsequent mitigation of these hazards to eliminate them entirely or reduce them to an acceptable level.

The risks associated with the surgical implantation of the device, device use, and device failures are the same those observed for commercially available SCS devices. With an existing pre-market application approval for the commercially available RestoreSensor SureScan MRI and Intellis AdaptiveStim Neurostimulation Systems, an established safety profile of probable benefit outweighing risk already exists for SCS Therapy for chronic back and/or leg pain. In most cases implantation of SCS is a reversible procedure and the system can be turned off or removed. Moreover, stimulation parameters are adjustable to minimize or reverse complications and maximize therapeutic effects. System output and programming parameters used with the proposed HD stimulation parameters are within the range of the commercially available RestoreSensor SureScan MRI and Intellis AdaptiveStim Neurostimulation Systems. However, some subjects may not receive effective pain relief with the proposed HD stimulation parameters. HD stimulation non-responders will be managed in the same manner as commercial patients, and their devices may be programmed to any combination of parameters chosen by their physician. The anticipated benefits of the clinical outcomes of SCS therapy per the study design outweigh the overall risk.

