### 13.3.7. Sensitivity analyses

Sensitivity analyses will be conducted for the primary efficacy objective using the methods described below:

- Completers analysis:
  - Only subjects in the Treated Analysis Set with complete paired data at the Baseline and 3-Month Visits will be included in the analysis.

█ [REDACTED]

█ [REDACTED]

[Redacted]

[Redacted]

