7.9.1.3. Analysis Methods

The two-sided, one sample t-test will be used to test the hypothesis of the primary objective with an alpha level = 0.05. The main analysis will include all subjects in the Treated Analysis Set. In addition to the hypothesis test, the two-sided 95% confidence interval for the average change in overall pain will be calculated and reported.

[Redacted text block]

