7.9.2.4. Analysis Methods

The analysis methods described in this section will be used for all secondary efficacy objectives.

The responder rate as defined for each secondary objective will be calculated for subjects in the Treated Analysis Set. The score (Wilson) method will be used to calculate the 95% confidence interval of the responder rate.

[Redacted content]

[Redacted content]

[REDACTED]

[REDACTED]

[Redacted]

[REDACTED]

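### Does the plan leave 3-month pain scores on HD settings mixed with scores on non-HD settings, with no way to tell how much that matters?

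*SAP*

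**What the plan says.** The purpose of the study (Protocol 4.2) is "to evaluate the efficacy of spinal cord stimulation (SCS) therapy using HD stimulation parameters" at a specific anatomical target. The primary objective (Protocol 5.1.1 and 13.3.1, SAP 4.1) is narrower than it may seem. It names HD parameters as the point from which stimulation starts and does not require subjects to stay on them until 3 months.

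The Treated Analysis Set (SAP 7.1.3) is defined by activation of the device. For the primary endpoint, SAP 7.9.1.3 says: "The main analysis will include all subjects in the Treated Analysis Set". For the secondary endpoints, SAP 7.9.2.4 says: "The responder rate as defined for each secondary objective will be calculated for subjects in the Treated Analysis Set". The one readable sensitivity analysis is the completers analysis in Protocol 13.3.7: "Only subjects in the Treated Analysis Set with complete paired data at the Baseline and 3-Month Visits will be included in the analysis".

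On programming, Protocol 9.8 allows unscheduled visits "to reprogram to optimize pain control (see Reprogramming Instructions in section 9.6), or for an AE". Protocol 10.4 says of HD non-responders that "their devices may be programmed to any combination of parameters chosen by their physician". For the Treated Analysis Set, SAP 7.7 evaluates programming data "to determine whether subjects ever received physician preference stimulation settings (ie, non-HD settings) during the study" and adds that "the months from Device Activation to first use of physician preference stimulation settings will be quantified".

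**The concern.** Readers will take the 3-month mean change and responder rates as results of HD stimulation. A subject who did poorly on HD, was moved to other settings before 3 months and then improved would count as a success of the strategy under study. Nothing in the readable efficacy sections separates such a score from one obtained on HD, and the completers analysis does not look at settings.

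The sponsor plainly foresees non-HD use after activation. Subjects who fail the device trial are exited, so the search in SAP 7.7 can only concern activated subjects. Calls at weeks 1, 3, 5 and 7 to 11 send subjects with inadequate relief to an unscheduled visit, so reprogramming before the 3-Month Visit is possible. If some of it leaves HD, the responder rates would overstate what HD alone achieved. The secondary objectives, which sized the study, would be affected most.

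**Working it through.** **1. The plan's own figures.** Inputs from SAP 6: two-sided alpha 0.05, mean change 20, SD 30, one-sample t-test. The noncentral-t calculation gives power 0.904 at N = 26 and 0.999998 at N = 100. The plan states 26 subjects for 90% power and over 99% at 100. The Wilson interval at 50% with N = 100 is 40.4% to 59.6%, half-width 9.6%, as stated. The planning figures are correct and not in dispute.

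**2. Where a settings-based analysis would stand.** Four places matter:
- Protocol 13.3.7: blacked-out items follow the completers analysis directly.
- Protocol 13.4.4: the contents list sensitivity analyses for the secondary objectives, and the responder-rate sections refer to them, but the text is blacked out.
- SAP 7.9.1.3 and 7.9.2.4: each is followed by blacked-out text.
- Protocol 9.6: the reprogramming instructions that 9.8 relies on are blacked out.

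The first three mean that absence from the readable text does not show absence from the plan. The fourth means that a permitted move to non-HD settings before 3 months is not shown either. Protocol 9.8 does not say that optimisation leaves HD. In the device trial the first reprogramming step stays within HD. Protocol 10.4 gives no timing, and SAP 7.7 covers the whole study.

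**3. What SAP 7.7 already provides.** Let *u* be the share of Treated subjects whose first non-HD use came before their 3-month score, *s* the share on non-HD settings at that score, and *r* the response rate among the latter. A subject whose first non-HD use came later was still on HD, so *s* ≤ *u*. A return to HD only makes *u* more cautious. Counting the switched subjects as non-responders lowers the responder rate by

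*s* × *r* ≤ *s* ≤ *u*.

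The months to first use, set against the visit dates, therefore cap the effect without any new variable.

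**4. Size, under assumed switch rates.** The documents give none. The range 5-20% switched with 30-50% responding is an assumption.

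| Share *s* | Drop at *r* = 30% | Drop at *r* = 50% | Largest possible drop |
|---|---|---|---|
| 5% | 0.05 × 0.30 = 1.5 points | 2.5 points | 5 points |
| 20% | 0.20 × 0.30 = 6 points | 0.20 × 0.50 = 10 points | 20 points |

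From a main rate of 50% (40.4% to 59.6%, N = 100), a drop of 1.5 points gives 48.5% (38.9% to 58.2%). A drop of 10 points gives 40.0% (30.9% to 49.8%).

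**5. Primary test.** Set the change of a share *s* to 0. The mean is 20(1 − *s*), and the variance is (1 − *s*)(30² + 20²) − mean².
- *s* = 0.05: mean 19; variance 0.95 × 1300 − 361 = 874; SD 29.6; power above 99.9%.
- *s* = 0.20: mean 16; variance 0.80 × 1300 − 256 = 784; SD 28.0; power above 99.9%.
- *s* = 0.40: mean 12; variance 0.60 × 1300 − 144 = 636; SD 25.2; power 99.7% (97.7% if the SD is held at 30).

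A value of 0 is not a strict lower bound. For a subject whose pain worsened, replacing a negative change by 0 raises the mean.

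**6. Cost of restricting to HD.** Dropping switched subjects would work against the precision target of ±10%. At 50%, 93 subjects give a half-width of 9.96% and 92 give 10.01%, so losing 8 of 100 misses the target. Keeping all Treated subjects protects it.

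**The case for a change.** The strongest case for the concern is this. SAP 7.7 shows that the sponsor expects some activated subjects to leave HD. Ever-use counts switches after 3 months, and months to first use does not show a return to HD. Neither quantity identifies the setting active at the 3-month score, and neither is tied to an efficacy result in the readable text. Initial and final interrogation reports are already required at each clinic visit, so a flag for the active setting would be cheap. At the top of the assumed range, the 10-point shift slightly exceeds the planned half-width of 9.6 points.

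Part of this stands. No settings-based efficacy analysis can be read in either document, and SAP 7.7 does not commit to tabulating first use before the 3-Month Visit. Such a table would be a reasonable supplement.

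It does not make the plan deficient. The supplement may already be in the blacked-out sensitivity analyses. The active-setting flag would tighten a cap that the SAP 7.7 data already allow, and would not supply something otherwise unobtainable. The 10-point figure needs two assumptions together, one in five switched and half of them responding, and neither has support in the documents.

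**Conclusion.** The concern does not hold. A missing settings-based analysis is not established, and neither is a permitted move to non-HD settings before 3 months, because the relevant text in both documents is blacked out. Including all Treated subjects is a treatment-policy analysis that matches an objective framed as stimulation starting at HD parameters. The secondary rates are characterised without testing.

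The possible effect is on interpretation: 1.5-10 points on a responder rate under the assumed 5-20% switched and 30-50% responding, and nothing if nobody is off HD at 3 months. The primary test is practically unaffected. The cap from SAP 7.7 assumes that the programming uploads are complete enough to date the first non-HD use. On that basis the plan as written gives no wrong result and needs no change.

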7.8. Interim Analyses

No interim analyses are planned in this study to assess the primary objective endpoint. Interim analyses providing preliminary characterization of the secondary objectives and some additional measures may be performed prior to the analysis of the primary objective. No statistical adjustments will be made for these interim analyses, as formal hypothesis testing will not be conducted. [REDACTED]

7.9. Evaluation of Objectives

7.9.1. Primary Objective

The primary objective is to demonstrate a significant improvement in overall (low back and leg) pain intensity, as measured by the Visual Analog Scale (VAS), from Baseline to the 3-Month Visit.

7.9.1.1. Hypothesis

The mean change in overall pain in implanted subjects (μ_c) from baseline to 3 months will be statistically significantly different from no change on the VAS scale 0-100 mm:

$$H_0: \mu_c = 0$$

$$H_A: \mu_c \neq 0$$

7.9.1.2. Endpoint Definition

The change in overall pain will be calculated for all subjects in the Treated Analysis Set as:

$$\text{Baseline overall pain} - \text{3-Month overall pain}$$

The baseline and 3-month overall pain scores will be collected on the VAS at the Baseline and 3-Month Visits, respectively.

7.9.1.3. Analysis Methods

The two-sided, one sample t-test will be used to test the hypothesis of the primary objective with an alpha level = 0.05. The main analysis will include all subjects in the Treated Analysis Set. In addition to the hypothesis test, the two-sided 95% confidence interval for the average change in overall pain will be calculated and reported.

[Redacted text block]

7.9.2. Secondary Objectives

7.9.2.1. Secondary Objective 1: Overall pain responder rate

This secondary objective is to characterize the overall (low back and leg) pain efficacy responder rate, as measured by the VAS, from Baseline to the 3-Month Visit, with a confidence interval within $\pm 10\%$.

Endpoint definition

The responder rate will be calculated as the proportion of subjects in the Treated Analysis Set who demonstrate at least a 50% improvement in overall pain from baseline to 3 months. For each subject, percentage improvement will be calculated as:

$$\frac{(\text{Baseline overall pain} - \text{3-Month overall pain}) \times 100}{\text{Baseline overall pain}}$$

The baseline and 3-month overall pain scores will be collected on the VAS at the Baseline and 3-Month Visits, respectively. Subjects who report at least a 50% improvement in overall pain will be considered responders.

7.9.2.2. Secondary Objective 2: Low back pain responder rate

This secondary objective is to characterize the low back pain efficacy responder rate, as measured by the VAS, from Baseline to the 3-Month Visit, with a confidence interval within $\pm 10\%$.

Endpoint definition

The responder rate will be calculated as the proportion of subjects in the Treated Analysis Set who demonstrate at least a 50% improvement in low back pain from baseline to 3 months. For each subject, percentage improvement will be calculated as:

$$\frac{(\text{Baseline low back pain} - \text{3-Month low back pain}) \times 100}{\text{Baseline low back pain}}$$

The baseline and 3-month low back pain scores will be collected on the VAS at the Baseline and 3-Month Visits, respectively. Subjects who report at least a 50% improvement in low back pain will be considered responders.

7.9.2.3. Secondary Objective 3: Leg pain responder rate

This secondary objective is to characterize the leg pain efficacy responder rate, as measured by the VAS, from Baseline to the 3-Month Visit, with a confidence interval within $\pm 10\%$.

Endpoint definition

The responder rate will be calculated as the proportion of subjects in the Treated Analysis Set who demonstrate at least a 50% improvement in leg pain from baseline to 3 months. For each subject, percentage improvement will be calculated as:

$$\frac{(\text{Baseline leg pain} - \text{3-Month leg pain}) \times 100}{\text{Baseline leg pain}}$$

The baseline and 3-month leg pain scores will be collected on the VAS at the Baseline and 3-Month Visits, respectively. Subjects who report at least a 50% improvement in leg pain will be considered responders.

7.9.2.4. Analysis Methods

The analysis methods described in this section will be used for all secondary efficacy objectives.

The responder rate as defined for each secondary objective will be calculated for subjects in the Treated Analysis Set. The score (Wilson) method will be used to calculate the 95% confidence interval of the responder rate.

[Redacted content]

[Redacted content]

[REDACTED]

[REDACTED]

[Redacted]

[REDACTED]

7.10. Safety Evaluation

7.10.1. Adverse Events and Device Deficiencies

In this study, only device-, therapy- and procedure-related adverse events (AEs) and device deficiencies that occur from enrollment through subject discontinuation from the study will be collected. All AEs and device deficiencies will be summarized.

Adverse events and device deficiencies will be summarized by study phase (e.g., Pre-Trialing, Trialing, Implant), with the appropriate number of corresponding subjects as the denominator within each study phase as described below.

Adverse events and device deficiencies, referred to as “events” within this section, will be summarized separately. Events will be coded and summarized using the Medical Dictionary for Regulatory Affairs (MedDRA). Summaries will be presented as the number of events, the number of serious events (for adverse events only), the number of subjects who experienced the event, and the percent of subjects who experienced the event.

Each event summary will be presented in 2 ways (separate tables) using MedDRA’s coding system:

- (1) By MedDRA System Organ Class (SOC) and Preferred Term (PT), sorted first by the recommended SOC order, then in descending order within PT by percent of subjects, number of events, number of serious events (for adverse events), and then alphabetically by PT

- (2) By MedDRA PT, sorted in descending order by percent of subjects, number of events, number of serious events (for adverse events), and then alphabetically by PT.

Each adverse event is evaluated for whether it qualifies as an Unanticipated Serious Adverse Device Effect (USADE). All USADEs will also be summarized separately by study phase as described below. If no USADEs occur, a statement indicating that will be included.

In addition to the summaries above, device deficiencies may also be summarized by device type and PT. Detailed listings of all adverse events and device deficiencies will be included in the final study report.

